### **5.3.5. Subject Replacement**

Subjects that have discontinued the study prematurely will not be replaced. New inhabitants that move into the study area will be approached for consent during the study.

### **5.3.6. Termination of Study**

The study's safety data will be analyzed by the DSMB after the interim analyses conducted soon after the 2nd MDA, and another conducted after the first full season of treatment. A detailed plan for interim analysis, any planned statistical adjustments to be employed as a result of interim analysis, the provisional stopping rules and how the stopping rules will be applied, will be drawn up prior to the start of the interim analysis.

Following the recommendation from the DSMB, the sponsor reserves the right to temporarily suspend or prematurely discontinue this study at any time for reasons including, but not limited to, safety or ethical issues or severe non-compliance. If the sponsor determines such action is needed, it will discuss this with the investigators. When feasible, the sponsor will provide advance notification to the investigator of the impending action prior to it taking effect. The sponsor will promptly inform the DMID/NIH, the CSU and Yale IRBs and the Comité d'Ethique of the IRSS, and provide the reason for the

suspension or termination. The study may also be suspended or terminated at the discretion of the DMID/NIH based on funding decisions.

If the study is prematurely terminated by the sponsor, any regulatory authority, or the investigator for any reason, the investigator will promptly inform the study subjects and assure appropriate therapy or follow-up for the subjects, as necessary. The investigator will provide a detailed written explanation of the termination to the IRBs and IEC.

---

## 6. STUDY INTERVENTION/INVESTIGATIONAL PRODUCT

### 6.1. Study Product Description

#### 6.1.1. Acquisition

##### Product 1 – generic IVM

IVM (generic IVM, 6 mg tablets) will be purchased either from Laboratorio Elea, Argentina, who also produced these for the IVERMAL trial (48), or from another supplier. These will be shipped from the production facility to Burkina Faso with a tracking number on a commercial transport service, and transported to the study site with all the required regulatory documents. Electronic temperature monitors will be included during shipping and transport to ensure the quality of the product is not compromised during shipment.

##### Product 2 - placebo

Placebo (e.g. sucrose) will be purchased from either from Laboratorio Elea, Argentina, who also produced these for the IVERMAL trial (48), or from another supplier. These will be shipped from the production facility to Burkina Faso with a tracking number on a commercial transport service, and transported to the study site with all the required regulatory documents. Electronic temperature monitors will be included during shipping and transport to ensure the quality of the product is not compromised during shipment.

#### 6.1.2. Formulation, Packaging, and Labeling

##### Product 1 –generic IVM

See the package insert.

##### Product 2 - placebo

To be determined by the manufacturer.

### 6.1.3. Product Storage and Stability

#### Product 1 – generic IVM

Per the package insert, the product will be maintained in a climate-controlled study drug storage room that is <30°C and free from high humidity. When traveling to the villages, the product will be kept in cool boxes during transport.

#### Product 2 - placebo

Similar to the package insert, the product will be maintained in a climate-controlled study drug storage room that is <30°C and free from high humidity. When traveling to the villages, the product will be kept in cool boxes during transport.

## 6.2. Dosage, Preparation and Administration of Study Intervention/Investigational Product

IVM or IVM placebo will be given monthly from July-October (4X) over 2 consecutive seasons as a 3-day course to all eligible persons per exclusion/inclusion criteria. Similar to the Mectizan and Iver P package inserts, dosing of IVM or placebo will be according to height as an estimate for weight (Table 5)

**Table 4: Dosing of ivermectin or placebo**

Height (cm)	Estimated weight (kg)	# of Tablets	Total mg per dose	Total mg per 3-day course
90-119	15-25	1 tablet	6mg	18mg
120-140	26-44	2 tablets	12mg	36mg
141-158	45-64	3 tablets	18mg	54mg
>158	65-84	4 tablets	24mg	72mg

The study pharmacist (who will be unblinded) will allocate the IVM and placebo tablets for each IVM MDA round according to the original randomization throughout the trial, and distribute the drug in sealed containers labeled by the codes “Village X(1-7) – Arm 1” and “Village Y(1-7) – Arm 2” to the clinical team no more than 2 days prior to each round.

### 6.3. **Modification of Study Intervention/Investigational Product for a Subject**

If the 3x300 µg/kg dose (estimated by height) schedule is observed to incur drug-related AE (see section 2.3.1 and Appendix B for known drug-related AE) in more than 10% of the treated population after the first MDA by the study physician, the dosing schedule may be modified to a 1x400 µg/kg dose (estimated by height) schedule each month for the remainder of the trial. This would only change the number of consecutive days a dose of ivermectin (or placebo) would be given per MDA, from 3 consecutive days per MDA to only once per MDA (see Table 5); it would not change the number of tablets or the total mg per dose corresponding to each height band. This change in dosing will be done in an online or phone ad hoc consult with the DSMB in the month after the 2nd MDA, and may depend on the follow-up clinical evaluations of participants. The clinical reasons for this change will be written into a report authored by study physician prior to the next MDA and will be sent to the IRBs/EC, CRO and to the DMID prior to the next MDA.

If an individual participant is determined unable to take a dose of IVM/placebo due to a known allergy to the drug or other reason, the product or dosage will not be modified in any way. Instead, this and/or all future doses will not be administered to the participant and this will be noted accordingly on the participant's case report form.

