#### 8.4. Halting Rules

Interpretation of results and decisions about discontinuation of any treatment arms will be made by the DSMB, using the suggested guidelines given here. We do not propose that the DSMB be strictly bound by pre-specified criteria, because of the complexity of the trade-offs between safety, efficacy, and costs of the intervention, and the possibility that new information from contemporaneous ivermectin trials will change considerations. Rather, consideration of stopping guidelines requires a reasoned judgment based on all information that is available at the time of data review. As this is a double-blind, placebo-controlled study that uses malaria incidence as the primary outcome, it will not be possible to accurately-measure the expected, modeled effect size (Figure 4, ~43%) until the end of the second treatment season (after MDA 8). Therefore, interim analysis of superiority of effect size in one blinded arm over the other will not be available in an appropriate timeframe to stop the study over the course of the two-year intervention. Furthermore, important secondary outcomes that ideally need 2 seasons of intervention are designed to determine if repeated ivermectin MDA treatment affects ACT resistance in malaria parasites and the possible development of ivermectin resistance in mosquitoes.

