Instead, the interim analyses of safety (AEs), relative to the expected benefits in possible reduced malaria incidence in the cohort and reduced NTD among the treated populace, will provide the main data points for consideration of early halting of the trial. The expected AE incidence of the present study can be estimated from the RIMDAMAL I and IVERMAL trials, and used to decide if drug-related AE incidence is abnormally high relative to the expected benefit. The RIMDAMAL I trial had a dosing regimen of 150-200 µg/kg every 3 weeks for 18 weeks (6 treatments) to eligible participants in villages of the same region as this study. This resulted in AE being observed in 3% of the entire population of the study arm (45 AE in 1447 participants). However only ~75% of these participants were repeatedly treated with drug in the arm, and only 5 of these AE were considered possibly or probably related to the intervention (5/787 treated participants; 0.6%). All were classified as standard AE (see Appendix B) of mild or moderate intensity that consisted of vomiting, pruritus, edema in the limbs, or tremors. In the IVERMAL trial, 48 adult participants with confirmed symptomatic uncomplicated *Plasmodium falciparum* malaria were treated with one dose of an ivermectin regimen consisting of 3 days of 300 µg/kg/day that was co-administered with a 3-day course of dihydroartemisinin-piperaquine. This resulted in 8% (4/48) participants having an AE, but only 4% (2/48) of which were considered treatment-related. These AE were minor visual disturbances. Neither trial observed any treatment-related SAE.

Each round of MDA is given to the entire study population over the course of 3 days. Data on AEs/SAEs will accumulate over the course of the month following each MDA, and data will be entered into the eCRFs. Thus, the data at the end of each round of MDA should capture all enrolled individuals by either active or passive follow-up. The study team will review these data on an ongoing basis for any concerning safety signals. It is anticipated that the first full safety review of the initial round of MDA will

---

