occur around between the 2nd and 3rd MDA round due to the time it will take to input and collate data. At the time of this review, and all others, it is recommended that if treatment-related AEs (Grade 2 or above) occur in 10% of the treated participants in the intervention arm, or if treatment-related SAE occur in 2% of the treated participants in the intervention arm, the following will take place:

- The dose of IVM will be reduced to a 1x400 µg/kg dose (see section 6.3).
- The DSMB should immediately convene an ad-hoc meeting that considers both unblinded safety data, as well as efficacy data (modeled and actual effect size of the primary outcome), to consider whether the study should be halted early or continue with a 1x400 µg/kg dose.

The DSMB will have a scheduled meeting between the 2nd and 3rd MDA round, and after the completion of 1st rainy season. At this point, the DSMB will review all safety data to determine if dose modification is potentially warranted.

Following recommendation from the DSMB, the sponsor reserves the right to temporarily suspend or prematurely discontinue this study at any time for reasons including, but not limited to, safety or ethical issues or severe non-compliance. If the sponsor determines such action is needed, it will discuss this with the investigators. When feasible, the sponsor will provide advance notification to the investigator of the impending action prior to it taking effect. The sponsor will promptly inform the DMID/NIH, the CSU and Yale IRBs and the Comité d’Ethique of the IRSS, and provide the reason for the suspension or termination. The study may also be suspended or terminated at the discretion of the DMID/NIH based on funding decisions.

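### Sections 6.3 and 8.4 state different triggers for one dose reduction without saying how they relate, and the fallback labelled 1x400 µg/kg is one day of the tablets labelled 300 µg/kg/day

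*Protocol*

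**What the plan says.** **Trigger in Protocol 6.3.** The schedule can be cut from 3x300 to 1x400 µg/kg if drug-related AEs are seen "in more than 10% of the treated population after the first MDA by the study physician, the dosing schedule may be modified". No grade is set, no SAE limit is given, and the arm is not named. The route is through the DSMB: "This change in dosing will be done in an online or phone ad hoc consult with the DSMB in the month after" the second MDA.

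**Trigger in Protocol 8.4.** For the same reduction, with a cross-reference to 6.3, the first condition is that "treatment-related AEs (Grade 2 or above) occur in 10% of the treated participants in the intervention arm". The alternative condition concerns serious events only: "or if treatment-related SAE occur in 2% of the treated participants in the intervention arm". The rule applies repeatedly and as a recommendation: "At the time of this review, and all others, it is recommended that". Once it is met, the text says that the dose *will* be reduced and that the DSMB should meet ad hoc to decide between halting and continuing at 1x400. That meeting is to weigh unblinded safety data "as well as efficacy data (modeled and actual effect size of the primary outcome"). Section 8.4 describes its own status as advisory: decisions on discontinuing an arm "will be made by the DSMB, using the suggested guidelines given here".

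**Fallback dose.** Sections 2.3.1, 6.3 and 8.4 all call it 1x400 µg/kg. Section 6.3 adds that only the number of days changes, from three to one; tablets and milligrams per dose in each height band stay as in the dosing table (Table 4). The main regimen with those tablets is labelled 300 µg/kg/day throughout. Section 2.3.1 says that preliminary modelling of the fallback showed a loss of just under a week of mosquito-killing activity.

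**The concern.** A safety threshold that leads to a dose change should have one reading. Here the grade, the SAE limb, the denominator, the timing and the force (*may* against *will*) all differ between two sections that govern the same action, and nothing explains the difference. The grade cut-off is a likely place for the two to part. Of the related AEs in the earlier village trial, section 8.4 reports: "All were classified as standard AE (see Appendix B) of mild or moderate intensity". Any mild events of that kind would count under 6.3 and not under 8.4.

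The denominator matters because the trial is blinded. Placebo recipients also take study tablets, so they can be read as treated. Section 6.3 rests on what the study physician observes, while the person whom the protocol names as unblinded is the pharmacist (6.2, 6.4).

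The label matters because 8.4 asks the DSMB to choose between stopping and continuing at 1x400, with modelled efficacy among its inputs. One tablet count cannot be nominally 300 µg/kg when given for three days and 400 µg/kg when given once. Section 2.1 treats 400 µg/kg as a distinct, higher dose.

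**Working it through.** **Inputs.** About 2,500 participants per arm, about 75% receiving MDA (treatment-arms table in the Protocol Summary); 6 mg tablets, 1 to 4 per dose, with estimated weights of 15-25, 26-44, 45-64 and 65-84 kg (Table 4); earlier related-AE rates of 5/787 and 2/48 (8.4). The rates in cases A to C are illustrations, not forecasts.

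**1. Size of each trigger.**
- Treated per arm: 0.75 × 2,500 = 1,875; both arms: 3,750.
- 8.4: 10% of 1,875 = 187.5, so about 188 people with related Grade 2+ AEs; or 2% = 37.5, so about 38 with related SAEs.
- 6.3, one arm: more than 187.5, so about 188 people with a related AE of any grade. Both arms: more than 375.
- With the Summary's total of about 4,700 instead, treated per arm is 0.75 × 2,350 = 1,762.5, and the 10% bars become about 176 and 353.
- If 6.3 pools the arms and the placebo rate is p0, the ivermectin rate must exceed 20% − p0: 20% at p0 = 0, 15% at p0 = 5%.
- If a share g of related AEs is Grade 2+, the AE limb of 8.4 is met at an any-grade rate of 10%/g: 20% at g = 50%, and 10% to 40% for g from 100% to 25%. The documents do not give g.

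**2. Where the two part.**

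| Ivermectin arm after MDA 1 | 8.4 | 6.3, ivermectin only | 6.3, both arms |
|---|---|---|---|
| A: related Grade 1 only, 15% (281) | not met | met | met only if placebo > 5% |
| B: related SAEs 2% (38), any related AE 5% (94) | met | not met (5.0%) | not met (94/3,750 = 2.5% with none on placebo) |
| C: related Grade 2+ 15% (281), placebo 1% (19) | met | met | not met (300/3,750 = 8.0%) |

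For scale, 5/787 = 0.64% is about 12 people in 1,875, and 2/48 = 4.17% is about 78. Neither trigger would be met.

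**3. What the fallback delivers.** First the plan's own figures: 3 × 6, 12, 18 and 24 mg = 18, 36, 54 and 72 mg per course, as in Table 4. Then dose = mg × 1,000 / kg:

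| Height (cm) | mg | Lightest | Midpoint | Heaviest | Midpoint below 400 |
|---|---|---|---|---|---|
| 90-119 | 6 | 400 | 6,000/20 = 300 | 240 | 25% |
| 120-140 | 12 | 462 | 12,000/35 = 343 | 273 | 14% |
| 141-158 | 18 | 400 | 18,000/54.5 = 330 | 281 | 17% |
| >158 | 24 | 369 | 24,000/74.5 = 322 | 286 | 19% |

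The tablets give 400 µg/kg or more only at 15 kg, 26 to 30 kg and 45 kg, and never in the tallest band. A true 400 µg/kg at the midpoints would need 0.4 × kg / 6 = 1.3, 2.3, 3.6 and 5.0 tablets.

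**4. Cut in the monthly course.** By the labels: 1 − 400/900 = 55.6%. By the tablets: 1 − 1/3 = 66.7%.

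**The case against.** The strongest reply is that the triggers form two coherent tiers. Section 6.3 sets a lower bar for an optional step. Section 8.4 sits under halting rules and sets a higher bar for a firmer step, with a meeting on whether to stop. A reader might infer that the protocol contradicts itself or could give opposing instructions. The documents do not support that. Section 6.3 does not say that the dose may be reduced *only* on its own condition, so in case B nothing forbids the reduction. In case A a permitted step is simply not recommended. One DSMB handles both, in the same window (6.3 in the month after the second MDA, 8.4 between the second and third), and 8.4 says that it is not strictly bound by its criteria. Sections 5.3.6 and 10.3.1 leave operating detail to an interim plan and a DSMB charter that are not among the documents and may settle the matter. All of this stands. What remains is that the protocol never states the tiers and never says whose denominator 6.3 means. The containers carry coded arm labels, so a count by arm is possible, but 6.3 does not ask for one.

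On the label, the reply is that height-band dosing is approximate, that 400 lies inside the 240-462 µg/kg range, and that nobody could give the wrong tablets because 6.3 spells out the change. That last part is right: a risk of misdosing does not follow. Nor can one infer that the DSMB would be shown modelling of the wrong dose, since 2.3.1 does not say which dose was modelled. But the approximation applies equally to the main regimen, which the same tablets label as 300, so it does not justify a second figure.

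**Conclusion.** The point holds as two wording faults, and it is minor. First, one dose reduction has a permissive trigger and a recommended trigger that differ in grade, SAE limb, denominator and timing. They are compatible, but their relation is unstated, and 6.3's denominator can double the count needed (about 188 against 375, assuming about 1,875 treated per arm). Second, the 1x400 µg/kg label is wrong as written. The fallback is one day of the dose labelled 300 µg/kg/day, about 300 to 343 µg/kg if people weigh the midpoint of their band (actual weights are not given). The two-thirds cut in the course needs no weight assumption.

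There is no effect on power or the primary analysis, the physical action is clear, and the earlier related-AE rates would meet neither trigger.

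**What to change.** - Make 8.4 the governing trigger: related Grade 2+ AEs in 10%, or related SAEs in 2%, of treated intervention-arm participants, assessed by the DSMB on arm-level data. Have 6.3 refer to it. Alternatively, state that 6.3 is a permissive lower tier and name its denominator.
- Relabel the fallback in 2.3.1, 6.3 and 8.4 as one day of the same height-band dose (nominal 300 µg/kg). If 400 µg/kg is really intended, add a tablet table for it.
- Confirm in 2.3.1 which dose the modelled loss of activity refers to.
- Check that the DSMB charter and interim plan match.

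The cost is a wording change and a check of the charter, the interim plan and the modelling input, with no new data, analysis or sample size. Which threshold and which dose are right is for the sponsor's clinicians and the DSMB.

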## PROTOCOL SUMMARY

Title:	Repeat Ivermectin Mass Drug Administrations for MALaria Control II (RIMDAMAL II): a double-blind, cluster-randomized control trial for integrated control of malaria.
Phase:	3
Population:	14 villages, 2 arms (7 clusters/arm); all healthy and eligible participants (both genders and all ages), approximately 4,700 people who live in southwestern Burkina Faso
Number of Sites:	1 site in southwestern Burkina Faso
Study Duration:	3 years (between 2018-2021)
Subject Participation Duration:	2.5 years (2019-2021)
Description of Agent or Intervention:	generic ivermectin, 6 mg tablet; dose: 3-day oral regimen of 300 µg/kg/day estimated by height bands, administered monthly for 4 months/rainy season over 2 consecutive rainy seasons.
Objectives:	
Primary:
 

• To assess the impact of a combined approach of repeated IVM MDA and SMC on malaria incidence in children, with the purpose of testing the superiority of IVM compared to placebo for reducing malaria incidence. Our hypothesis that IVM MDAs (the intervention), coinciding with standard of care antimalarial procedures in Burkina Faso (four SMC rounds during the rainy season, maximum LLIN coverage and IPTp for pregnant women), will significantly reduce the incidence of childhood malaria in the intervention arm compared to the control arm. The IVM MDAs will consist of generic IVM or IVM placebo (e.g. Iver P®, Elea Labs; 6 mg tablet) given monthly

from July-October (4X) as a 3-day course to all eligible persons who meet inclusion criteria ( $\geq 90$  cm and not treated with SMC ( $\geq 5$  years), not pregnant or breast feeding an infant less than 1 week old). Dosing of IVM or placebo will be according to height as indicated on the package: 90-119 cm = 1 tablet/day for 3 days; 120-140 cm = 2 tablets/day for 3 days; 141-158 cm = 3 tablets/day for 3 days;  $> 158$  cm = 4 tablet/day for 3 days.

Secondary:

- To measure whether the IVM MDAs will increase harms in the participants
- To measure the entomological indices (mosquito survival rate after blood feeding, mosquito population age structure, sporozoite rate if they are infected with *Plasmodium* parasites, human exposure to *Anopheles* mosquito bites) between the intervention and control arm and over the time of the intervention phase.

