Our study will administer the 3x300 µg/kg (estimated by height bands) regimen in 4-monthly rounds over 2 seasons and to approximately 1800 persons who are ≥90 cm height (and ≥ 5 years of age) in each study village. Thus, the greatest potential risk of this trial is in giving this dosing regimen more frequently (monthly x 4 months each season), to more participants, and to a broader range of age groups than in the IVERMAL trial. Because the length of mosquitocidal activity from this dosing regimen is a key determinant in the large expected effect size on malaria incidence (44), and also this 4-monthly schedule achieves logistic synergy with standard-of-care SMC treatment of children < 59 months old in the same households, an alternative to the 4-monthly treatment schedule may not be feasible relative to the project's goals. It may be possible to give a 1x400 µg/kg dose (estimated by height) schedule each month instead of the 3x300 µg/kg dose (estimated by height) schedule, if the latter is deemed as not well-tolerated after the first MDA. However, this change could affect our blinding, and preliminary modeling data we have obtained suggests a nearly a week less mosquitocidal activity would be achieved in the treated population, which would lessen the expected effect size considerably and so this may also not be feasible.

Other risks are minimal, and include psychological harm to study participants if their private information are disclosed, but we will make every effort to prevent this. Small bruising at the site of the finger stick and/or at the site of venipuncture are also possible, as is syncope from blood draws, but these procedures will all be conducted by the study clinical team who will be trained to treat these possible problems.

In summary, the risks to the subjects are moderate with respect to receiving the intervention (IVM MDA at the aforementioned dose and frequency) and minimal with respect to the clinical team taking blood samples or the investigators making public their personal information accidentally. These risks are reasonable in relation to the anticipated benefit of significantly less malaria among the populace, which causes yearly debilitating disease and death in the communities in which we will work.

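### The safety fallback is labelled 1x400 µg/kg, but section 6.3 keeps the 300 µg/kg/day tablets, so it is one third of the course: a 67% cut, not the 56% the labels imply

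*Protocol*

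**What the plan says.** The Protocol Summary describes the intervention as a "3-day oral regimen of 300 µg/kg/day estimated by height bands". The dosing table in section 6.2 (captioned Table 4) has one set of amounts: 1, 2, 3 or 4 tablets of 6 mg per dose for the four height bands, with estimated weights of 15-25, 26-44, 45-64 and 65-84 kg. Its last column, headed "Total mg per 3-day course", lists 18, 36, 54 and 72 mg. No other tablet schedule appears in either document.

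Section 6.3 sets the fallback. If drug-related adverse events exceed 10% of the treated population after the first round, "the dosing schedule may be modified to a 1x400 µg/kg dose (estimated by height) schedule each month". The next sentence says that only the number of consecutive days changes, from three to one, and that "it would not change the number of tablets or the total mg per dose corresponding to each height band".

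Two other sections repeat the label without the tablet sentence:

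- Section 8.4 (Halting Rules) names the 1x400 µg/kg dose as the recommended reduction, with a cross-reference to 6.3. It then asks the DSMB, looking at unblinded safety data and at modelled and actual effect size, "to consider whether the study should be halted early or continue with a 1x400 µg/kg dose".
- Section 2.3.1 says "It may be possible to give a 1x400 µg/kg dose (estimated by height) schedule each month", and adds that "preliminary modeling data we have obtained suggests a nearly a week less mosquitocidal activity would be achieved in the treated population". It does not state the dose that was modelled.

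**The concern.** Two adjacent sentences of section 6.3 conflict. The same tablets, given on one day to the same height bands, cannot be nominally 300 µg/kg under the main regimen and 400 µg/kg under the fallback. Section 2.1 treats 400 µg/kg as a higher dose than the usual one, so the two figures are not used as synonyms.

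What is at stake is how the option is described to those who would weigh it. A DSMB member who takes the labels at face value would compare 900 µg/kg per round with 400 and conclude that 44% of the course is kept. The tablets keep 33%. Section 8.4 asks for that comparison at the point where the choice is between stopping the trial and continuing on the fallback. Section 6.3 also requires a written report of any dose change to the ethics bodies, the monitor and the funder, and the wrong figure could carry into it.

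**Working it through.** **Inputs.** Tablet strength is 6 mg (section 6.1.1). Tablets and estimated weights by height band come from the dosing table in section 6.2. The main regimen is 300 µg/kg/day for 3 days (Protocol Summary). The fallback is labelled 1x400 µg/kg, with tablets and mg unchanged and days reduced from 3 to 1 (section 6.3).

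**Step 1: the table's own figures.** Tablets × 6 mg gives 6, 12, 18 and 24 mg per dose. Three days give 18, 36, 54 and 72 mg. Both rows match the table.

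**Step 2: dose from one day of these tablets.** Dose (µg/kg) = mg × 1000 / weight (kg).

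| Height band | mg | Weights (kg) | Midpoint (kg) | Dose at midpoint | Range over band | Midpoint dose / 400 |
|---|---|---|---|---|---|---|
| 90-119 cm | 6 | 15-25 | 20 | 300 | 240-400 | 75% |
| 120-140 cm | 12 | 26-44 | 35 | 343 | 273-462 | 86% |
| 141-158 cm | 18 | 45-64 | 54.5 | 330 | 281-400 | 83% |
| >158 cm | 24 | 65-84 | 74.5 | 322 | 286-369 | 81% |

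No midpoint reaches 400.

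**Step 3: which label fits the tablets.** Weight at which the tablets give a stated dose = mg / dose.

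- For 300 µg/kg: 6/0.3, 12/0.3, 18/0.3 and 24/0.3 = 20, 40, 60 and 80 kg. Each lies inside its band.
- For 400 µg/kg: 6/0.4, 12/0.4, 18/0.4 and 24/0.4 = 15, 30, 45 and 60 kg. The first and third are the lightest edge of their bands, the second is inside its band, and the fourth is below the 65 kg at which its band starts.

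The table is a 300 µg/kg table.

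**Step 4: change in the course per round.**

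- By the labels: 3 × 300 = 900 µg/kg becomes 400 µg/kg. 400/900 = 44% kept, a 56% fall.
- By the tablets: three days become one at the same mg. 1/3 = 33% kept, a 67% fall.

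The 67% needs no assumption about weight. The 56% is not printed in the protocol; it is what its two labels imply.

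**Step 5: what a true 400 µg/kg would need.** Tablets at midpoint = 0.4 × weight / 6 = 1.33, 2.33, 3.63 and 4.97, rounding to 1, 2, 4 and 5. The lower two bands would still receive 300 and 343 µg/kg at midpoint. In the upper two bands the lightest listed weights would receive 24/45 = 533 and 30/65 = 462 µg/kg in one day.

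**The case against.** The strongest reply is that both labels are nominal. Each is described as a height-based estimate, the table prints no µg/kg figure, and light people in three of the bands do receive 400 or more, up to 462 at 26 kg. A person over 158 cm who weighs 60 kg or less would as well. The documents give no weight distribution, so the 300-343 figures rest on taking band midpoints as typical. This limits the precision of those figures. It does not reconcile the labels: whatever spread height banding produces is the same under both schedules, because the tablets are the same.

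The second reply is that nothing operational turns on it. This largely stands. Section 6.3 states the tablets, section 8.4 points back to 6.3, and anyone who reads the sentence after the label sees that three days become one. A reader might infer that staff could dispense the wrong dose; the documents do not support that. The fallback is also conditional. Section 8.4 puts drug-related events at 0.6% and 4% of treated participants in two earlier trials, against a trigger of about 10%. Section 6.3 says only that the schedule may be changed, and 8.4 says the DSMB is not strictly bound by the criteria. The SAP describes only the three-day regimen and refers to 2020 sampling in the past tense, so an amendment may have little remaining use in conduct.

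The third reply concerns the modelling. A reader might infer that the loss of mosquitocidal activity in section 2.3.1 is understated. That would follow only if the model was run at 400 µg/kg. If it used the actual tablets, only the label is wrong. The documents do not say which. A larger loss would also strengthen the argument made in 2.3.1, that the fallback may not be feasible. This is a question to ask, not an error shown.

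**Conclusion.** The label is wrong as written. The fallback is one day of the nominal 300 µg/kg dose: 300 to 343 µg/kg at the table's band midpoints (assuming midpoints are typical) and 240 to 462 µg/kg across its listed weights. It removes 67% of the course per round, against the 56% that the labels imply.

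The consequence is limited to how a safety option is described to those deciding on it. The error is conservative for safety: the single-day dose is no higher than on any day of the main regimen, and the course is smaller than the label suggests. The main regimen, the primary analysis and the sample size are untouched.

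A reader might also conclude that the label should be kept and the tablets raised to match. The documents do not support this. Section 6.3 expressly keeps the tablets, and the schedule in step 5 would raise the daily dose in the upper two bands as a response to adverse events, while still missing 400 at the lower two midpoints.

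**What to change.** In sections 6.3, 8.4 and 2.3.1, replace the 1x400 µg/kg label with: one day of the same tablets (6/12/18/24 mg by height band, nominal 300 µg/kg; one third of the 3-day course). Confirm that the modelling behind the loss of nearly a week in 2.3.1 used those amounts, and re-run it only if it used 400 µg/kg. Do not adopt a 1/2/4/5 tablet table.

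The cost is one phrase in three sections and a check of one model input. It is a small amendment, which section 13.2 requires the ethics bodies to approve before use. The fallback will look less effective to the DSMB than its present label suggests, but that is the accurate description.
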